## 7.3 LOST TO FOLLOW-UP

A participant will be considered lost to follow-up if they fail to return for 2 scheduled post-hospitalization visits and is unable to be contacted by the study site staff.

The following actions must be taken if a participant fails to return to the clinic for a required study visit:

- The site will attempt to contact the participant and reschedule the missed visit within 1 week and counsel the participant on the importance of maintaining the assigned visit schedule and ascertain if the participant wishes to and/or should continue in the study.
- Before a participant is deemed lost to follow-up, the investigator or designee will make every effort to regain contact with the participant (where possible, 3 telephone calls and, if necessary, a certified letter to the participant's last known mailing address or local equivalent methods). These contact attempts should be documented in the participant's medical record or study file.
- Should the participant continue to be unreachable, they will be considered to have withdrawn from the study with a primary reason of lost to follow-up.

# 8 STUDY ASSESSMENTS AND PROCEDURES

## 8.1 EFFICACY ASSESSMENTS

Study subjects will undergo the following procedures/evaluations:

- **Baseline assessments.** Medical history, surgical history, demographic features, height, weight, concomitant medication review and cumulative fluid balance, including previous exposure to blood transfusions, ADL survey.

- **Biological specimen collection and laboratory evaluations.** Following enrollment, study labs will be obtained according to table 1.3. CBC and creatinine is often done daily as standard of care. If the subject has a CBC and creatinine value obtained within the prior 24 hrs, this result may be used. However, if they received a unit of blood after that timepoint, the CBC would need to be repeated. All subjects will return for followup assessments and blood draws as noted in table 1.3. The research blood samples for storage and future research will be obtained (10 ml per subject) at enrollment and post-hospitalization assessments for future mechanistic studies. These samples will be cold-stored.
- **Administration of questionnaires or other instruments.** Subjects will undergo functional outcome assessments in accordance with the NHLBI-supported COMS of critical illness. These measures, either comprehensively or in part (as outlined in 1.3), will be obtained at enrollment, hospital discharge, and 1-month and 3-months post-hospitalization.

## 8.2 SAFETY AND OTHER ASSESSMENTS

Subjects will undergo the following procedures/evaluations:

- **Vital signs.** Temperature, pulse, respirations, blood pressure, continuous telemetry, oxygen saturations will be monitored during administration of iron and EPO for those in the intervention group as outlined in section 2.3. All subjects will receive standard ICU monitoring throughout their stay in the ICU.
- **Weight.** Subjects < 40 kg will be excluded due to unclear safety of 40,000 unit of EPO in persons with low weights
- **Assessment of adverse events.** Medical records will be reviewed daily for evaluation of adverse events. Adverse events will be indicated on the data forms for the study and on the specific adverse event report forms and all serious adverse events will be reported to the IRB within 24 hours of the research team learning about the event followed by a more detailed written report to the IRB. The following information about adverse events will be collected: 1) the onset and resolution of the event, 2) an assessment of the severity or intensity of the event, 3) an assessment of the relationship of the event to the intervention, and 4) any action taken because of event. The PI will report all potentially related SAEs to the DSMB and to NHLBI within 7 days of discovery.

## 8.3 ADVERSE EVENTS AND SERIOUS ADVERSE EVENTS

### 8.3.1 DEFINITION OF ADVERSE EVENTS (AE)

Adverse event means any untoward medical occurrence associated with the use of an intervention in humans, whether or not considered intervention-related (21 CFR 312.32 (a)).

As our subject population is by definition 'critically ill', it is expected that they will have many unrelated adverse health events during their hospital stay. Therefore, we will limit the scope of our adverse event monitoring and recording to focus on the following conditions:

- Study drug infusion reactions
- Venous thromboembolic disease
- Myocardial infarction
- Non-hemorrhagic stroke
- Bloodstream infections
- Hypertensive urgency or emergency in the 1 hour after study drug administration (i.e. SBP  $\geq$  200 or SBP increase by > 40 mmHg from the time of infusion start)

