**EPO** (i.e. Epoetin alpha), the erythropoiesis stimulating agent utilized in this trial, will be administered as a single 40,000 unit subcutaneous injection after iron supplementation, though iron supplementation will be withheld for those with ferritin > 1000 ng/ml. It has been used in previous clinical trials of anemia management in critical illness, and it is utilized in our current clinical practice for critically ill anemic and post-surgical patients with contraindications to transfusion therapies (i.e. Jehovah’s witness patients). There are short-term risks associated with this therapy, including minor non-allergic adverse reactions (nausea, dizziness, high blood pressure, pruritis; estimated <10%) and major rare adverse reactions (e.g. deep venous thrombosis, uncontrolled hypertension, myocardial infarction; estimated <1%). There is a black box warning for myocardial infarction, stroke, venous thromboembolism, vascular access thrombosis, and mortality when targeting hemoglobin levels >11 g/dL, data which is derived from repeated use of EPO to achieve near-normal hemoglobin levels for patients with chronic kidney disease. In a recent systematic review and meta-analysis of 21 trials in critical illness, the relative risk (RR) for mortality with EPO was 0.82 (95% CI 0.71-0.94). There were no significant differences in serious adverse events (RR 1.11, 95% CI 0.94-1.31) or VTE (RR 1.17, 95% CI 0.87-1.58), though these data do not exclude the potential for a clinically significant increase in the risk for adverse events with EPO therapy. As a longer-term risk, EPO may theoretically increase the risk of tumor progression or recurrence in patients with cancer. However, these concerns are derived from trials in non-surgical oncologic patients utilizing large doses of ESAs for extended periods of time, particularly when targeting normal hemoglobin levels. However, the

overwhelming evidence suggests that EPO use has no significant impact on cancer progression or other adverse oncologic outcomes, particularly when used in low-doses and when pre-treatment hemoglobin concentrations do not exceed 12 g/dL. To this end, EPO is used extensively for preoperative anemia management in patients undergoing oncologic surgery. Additionally, EPO is now recommended for the treatment of anemia in critical ill adults by the French Society of Anesthesia & Intensive Care Medicine (SFAR).

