  - b. Anemias requiring erythropoietic stimulation. This includes anemia not secondary to acute blood loss or iron deficiency (e.g. anemia of inflammation, anemia of renal disease). Etiology will be determined immediately *prior to randomization* upon review of laboratory values (i.e. iron studies) and clinical history (i.e. admission diagnoses, surgery/acute blood loss) with treatment decisions adjudicated pre-randomization by the PI and trial Co-I's should the PI be unavailable.
    - Patients without iron-responsive anemias will receive a single dose of 40,000 units of subcutaneous EPO (Retacrit). For those with ferritin less than 1000 ng/ml they will also receive 1000 mg IV iron prior to EPO administration to replenish usable iron, given that iron will

invariably be mobilized secondary to EPO stimulation. EPO will be given in accordance with Mayo Clinic administration guidelines.

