#### 8.3.4 TIME PERIOD AND FREQUENCY FOR EVENT ASSESSMENT AND FOLLOW-UP

The occurrence of an adverse event (AE) or serious adverse event (SAE) may come to the attention of study personnel during study visits and interviews of a study participant presenting for medical care, or upon review by a study monitor.

As noted earlier, for this study we plan to observe for a specific set of AEs and this information will be captured on the appropriate case report form (CRF). Information to be collected includes event description, time of onset, clinician’s assessment of severity, relationship to study product (assessed only by those with the training and authority to make a diagnosis), and time of resolution/stabilization of the event. All AEs will be followed to adequate resolution.

Changes in the severity of an AE will be documented to allow an assessment of the duration of the event at each level of severity to be performed.

Study coordinators will record all listed reportable events with start dates occurring any time after informed consent is obtained through 3-months after hospitalization. At each study visit, the investigator will inquire about the occurrence of AE/SAEs since the last visit. Events will be followed for outcome information until resolution or stabilization.

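### The list of adverse events to be recorded does not match the EPO risks the protocol names: vascular access thrombosis is missing and stroke is narrowed to non-hemorrhagic

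*Combined protocol and SAP*

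**What the plan says.** Section 8.3.1 opens with a broad regulatory definition of an adverse event. It then argues that ICU patients have many unrelated events, and narrows the task: "we will limit the scope of our adverse event monitoring and recording to focus on the following conditions". Six conditions follow: reactions to the study-drug infusion, "Venous thromboembolic disease", myocardial infarction, "Non-hemorrhagic stroke", bloodstream infection, and a marked blood-pressure rise in the hour after dosing.

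Section 8.3.4 repeats the limit twice: "for this study we plan to observe for a specific set of AEs", and "Study coordinators will record all listed reportable events with start dates occurring any time after informed consent is obtained through 3-months after hospitalization". Section 8.3.8 marks events of special interest as not applicable, so there is no second list.

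On the risk side, section 2.3.1 states: "There is a black box warning for myocardial infarction, stroke, venous thromboembolism, vascular access thrombosis, and mortality when targeting hemoglobin levels >11 g/dL". Section 9.4.4 promises that all AEs and SAEs, with mortality and readmission, will be compared between the arms.

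**The concern.** A short, targeted list is a reasonable choice in an ICU trial, where recording everything would bury the signal. But a targeted list should contain the drug risks that the same protocol sets out. Here one boxed-warning outcome is left out and another is cut down.

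What is at stake is the safety comparison. The trial is open-label, has about 50 patients per arm, and is meant to inform a larger trial (sections 4.2 and 9.4.9). If an event type is not named, whether it enters the tables depends on someone judging it serious, unexpected or related. Such judgments can differ between an arm that received EPO or iron and an arm that received neither.

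**Working it through.** The check compares texts; the plan gives no figure to reproduce on this point.

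**1. Boxed-warning outcomes (section 2.3.1) against the list (section 8.3.1)**

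| Outcome named in 2.3.1 | On the 8.3.1 list? |
|---|---|
| Myocardial infarction | Yes |
| Venous thromboembolism | Yes |
| Stroke, type not stated | In part: non-hemorrhagic only |
| Vascular access thrombosis | No |
| Mortality | Not listed, but an endpoint to 12 months and part of 9.4.4 |

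Of five outcomes, two are listed in full, one in part, one is covered elsewhere as an endpoint, and one is absent.

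**2. Other arterial thrombosis.** Section 2.3.1 does not name it. Section 5.2, criterion 7, gives acute arterial thrombus as an example of excluding thrombosis. It waives the criterion for acute blood loss anemia, the group that section 6.1.1 treats with iron alone. The table in section 2.3.3 gives added EPO risk as the reason for excluding thrombosis in general. The link to EPO is therefore a fair inference, but only an inference.

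**3. Do other clauses recover the missing events?**

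- *Section 7.1* says that any new clinically relevant finding is reported as an AE, without reference to the list. It sits in the section on stopping study drug and conflicts with 8.3.1 and 8.3.4, so staff have two rules.
- *Section 8.3.2* holds two SAE definitions. The opening paragraph turns on outcome alone (death, threat to life, hospitalization or its prolongation, incapacity). The bullets after it, which say how SAEs will be defined here, add conditions: related to study procedures, unexpected for the patient's acuity or ICU course, or beyond what critical illness normally brings. Prolonged hospitalization does not appear in the bullets.
- *Section 8.3.6* requires SAEs to be reported whether or not related, but only helps once an event qualifies under 8.3.2.
- *Section 8.3.3.3* calls an event unexpected when it is not consistent with the risk information already described. Access thrombosis is described in 2.3.1, so on that test its nature is already expected.

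**4. Who judges.** Relatedness is assessed by the examining clinician (8.3.3.2), and section 6.3 leaves clinicians unblinded. A control patient has received no study drug, so relatedness to it can hardly be found. The SAE route can therefore catch the same event in one arm and not in the other.

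**5. How many events.** The protocol gives no rate for access thrombosis, other arterial thrombosis or hemorrhagic stroke. The nearest figure is the estimate in 2.3.1 of under 1% for major rare EPO reactions. With 100 patients randomized 1:1, the intervention arm has 100 / 2 = 50. Taking the 1% bound, and assuming that all 50 received EPO, gives 50 × 0.01 = 0.5 event. Fewer than 50 will receive EPO, since the iron-responsive group gets iron alone. This bound concerns reactions attributed to the drug; it says nothing about background events in either arm.

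**The case against.** The strongest reply is that the list limits routine recording and does not redefine an AE. An intracranial hemorrhage or a limb-threatening arterial clot would ordinarily meet the opening paragraph of section 8.3.2 and be reported under 8.3.6. Records are reviewed daily (8.2), AEs and SAEs are asked about at each visit (8.3.4), and SAEs, deaths and readmissions are all compared (9.4.4). This stands as far as it goes. A reader might infer that these events would go wholly unrecorded, or that the safety table could never show an excess; the documents do not support that.

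Other parts of the reply also stand:

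- A reader might take arterial thrombosis as a risk that the protocol itself names for EPO. It is not, and two arterial events (myocardial infarction and non-hemorrhagic stroke) are listed.
- The stroke wording fits the protocol's reasoning. Section 2.3.3 gives cerebral ischemia as the concern, and section 5.2, criterion 10, excludes ischemic stroke. The case for hemorrhagic stroke rests on the unqualified word in 2.3.1 and on uncontrolled hypertension being named there as an EPO reaction.
- A reader might infer from the EPO group's definition ("This includes anemia not secondary to acute blood loss or iron deficiency (e.g. anemia of inflammation, anemia of renal disease") that dialysis-access patients are known to be among those treated. No section mentions dialysis or fistulas. Section 5.2 has no renal exclusion, so they may be enrolled, but criterion 1 removes anyone given an ESA in the previous 30 days.
- The boxed-warning data come from repeated dosing toward near-normal hemoglobin; this trial gives one dose.
- A venous catheter clot might be coded as venous thromboembolism, though 8.3.1 does not say so.
- The Data and Safety Monitoring Plan (10.1.6) is not part of the documents and might add events.

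None of this explains why access thrombosis is named as a risk and then left off the list, or settles which of the conflicting recording rules applies.

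**Conclusion.** The point holds as a minor one. Vascular access thrombosis is clearly missing, the narrowing of stroke is a lesser mismatch, and the absence of other arterial thrombosis is a reasonable addition by inference. Events that are non-serious, or serious but judged expected or unrelated, may go unrecorded or be recorded unevenly by arm, leaving the comparison in section 9.4.4 incomplete.

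This rests on reading 8.3.1 and 8.3.4 as the working rule for coordinators, and on the bullets in 8.3.2 being applied as the SAE definition. If staff instead follow 7.1 and the opening paragraph of 8.3.2, the gap is smaller.

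No size in percent should be put on it. A reader might posit one or two missed events and divide by an assumed number of EPO recipients, but the documents support neither figure, and few such events are expected.

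**What to change.** In section 8.3.1, for both arms and over the existing window from consent to 3 months after hospitalization:

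1. Replace the venous thromboembolism item with *venous or arterial thrombosis, including thrombosis of a vascular access or catheter*.
2. As a lesser point, replace the non-hemorrhagic stroke item with *stroke (record type: ischemic or hemorrhagic)*.
3. Reconcile sections 7.1, 8.3.1, 8.3.2 and 8.3.4, so that one rule says which events are recorded and which SAE definition applies.

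The cost is two changed lines, the matching fields on the AE form, a clarifying sentence or two, and a few extra events to document. Records are already reviewed daily for AEs. The change affects data collection only, not treatment.

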Briefly, this is a randomized clinical trial of a multifaceted anemia prevention and treatment bundle versus standard of care to assess the impact of the intervention on hemoglobin recovery and post-hospitalization functional outcomes. Each patient randomized to the intervention will receive 3 treatment components: 1) optimized phlebotomy practice; 2) clinical decision support; and 3) pharmacologic anemia treatment. With regards to pharmacologic anemia treatment, patients may receive either a single dose of intravenous (IV) iron therapy in isolation if they have an iron-responsive anemia or a single dose of EPO if they have an anemia of inflammation requiring erythropoietic stimulation. Further, some patients receiving EPO may also receive a single dose of IV iron to replenish iron stores prior to EPO administration

(i.e. if serum ferritin is < 1000 ng/ml at the time of randomization). Patients randomized to the standard of care arm will receive usual ICU cares.

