### 2.3.3 ASSESSMENT OF POTENTIAL RISKS AND BENEFITS

There is negligible patient risk associated with optimized phlebotomy and clinical decision support. Despite being used safely in multiple clinical trials in critical illness, there are tangible risks of IV iron and EPO therapies. Risks for pharmacologic anemia treatments (IV iron, EPO) will be minimized in multiple ways. First, we will exclude patients at highest risk for potential harm from these therapies, as outlined in the table below:

Exclusion Criteria	Rationale
Iron (IV) or Erythropoiesis-Stimulating Agents (ESA) use in 30 days prior to admission	Already receiving anemia treatment
Pregnancy or breastfeeding	Unclear safety of EPO
Weight <40 kg	Unable to standardize EPO dosing
Uncontrolled sepsis*	Potential infectious risk with IV iron
Allergy to IV iron or erythropoietin	Risk for allergic reaction
Inability to receive VTE pharmacoprophylaxis	Increased thrombosis risk with EPO
Suspected or active thrombosis or myocardial ischemia	Incremental risk with EPO
Uncontrolled hypertension (SBP $\geq$ 190 or DBP $\geq$ 110)	Risk for worsening with EPO
Stroke within 3 months prior	Risk for cerebral ischemia with EPO
Mechanical circulatory support devices (e.g. ECMO, ventricular assist device, Impella)	Risk for device thrombosis with EPO

Hb-hemoglobin. VTE-venous thromboembolism; SBP- systolic blood pressure; DBP-diastolic blood pressure.

\*Uncontrolled sepsis defined by <48 hours of appropriate antimicrobial therapy and/or lack of definitive source control, given theoretical risk for worsening infection with iron supplementation.

Additionally, pharmacological treatments will be targeted to the underlying etiology of anemia to enhance safety. For example, anemia in acute blood loss and iron deficiency is iron-restricted and likely to respond to iron supplementation

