#### 4.2 SCIENTIFIC RATIONALE FOR STUDY DESIGN

*This is a randomized parallel arm clinical trial comparing the multifaceted anemia intervention against control (standard care).* The control group will receive standard care without an active placebo for several reasons: 1) the multifaceted nature of the study intervention makes it difficult to design a placebo for each unique intervention element, particularly clinical decision support and optimized phlebotomy); 2) the expenses associated with administering a placebo for pharmacologic agents (i.e. iron, EPO) are considerable and would not be possible through the NIH K-23 funding mechanism; and 3) this is a pilot trial which will inform a larger, multi-center definitive clinical trial in which we would have the resources available for placebo administration of pharmacologic therapies. Superiority will be assessed as the goal is to improve anemia in the critically ill, given that the problem of anemia is extremely prevalent in the ICU, rather than to prove non-inferiority against standard care.

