#### 9.4.4 SAFETY ANALYSES

All AEs and SAEs will be presented and compared between groups. Mortality and hospital readmission rates will also be presented and compared between groups.

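### The hypertension adverse event can occur only in the active arm, yet it is to be compared between arms, and its blood pressure rule is loosely specified

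*Combined protocol and SAP*

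**What the plan says.** Section 8.3.1 narrows safety recording: "we will limit the scope of our adverse event monitoring and recording to focus on the following conditions". One of the six listed conditions is "Hypertensive urgency or emergency in the 1 hour after study drug administration". It is met by an SBP of 200 mmHg or more, or by "SBP increase by > 40 mmHg from the time of infusion start". No diastolic criterion is given, and no pressure that must be reached for a rise to count.

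On the control arm, section 2.2 says "Patients randomized to the standard of care arm will receive usual ICU cares", and section 4.2 says "The control group will receive standard care without an active placebo for several reasons".

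Section 9.4.4 says "All AEs and SAEs will be presented and compared between groups". It exempts no item and names no test.

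Elsewhere the protocol treats hypertension as an EPO risk:

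- Section 2.3.1 lists "major rare adverse reactions (e.g. deep venous thrombosis, uncontrolled hypertension, myocardial infarction; estimated <1" per cent, with no one-hour limit. The same sentence puts high blood pressure among minor reactions, estimated below 10%.
- The exclusion table in section 2.3.3 defines uncontrolled hypertension as SBP of at least 190 or diastolic pressure (DBP) of at least 110, with the rationale "Risk for worsening with EPO". The exclusion list in section 5.2 has no such criterion.
- Section 8.3.4 records listed events from consent to 3 months after hospitalization.

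**The concern.** An event timed from a drug that only one arm receives cannot measure a difference between arms. Under 9.4.4 the hypertension row would nevertheless sit in a comparative table, with some count in the active arm and zero in controls. A reader could take ordinary pressure swings in critically ill patients for a drug effect.

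The rule itself also works loosely in both directions. It can give the name of hypertensive urgency to a pressure that has merely recovered from a low value. It can also pass over pressures that the protocol elsewhere calls uncontrolled. The item bears on a named EPO risk, in a pilot meant to inform a larger trial.

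**Working it through.** The documents state no expected rate, power or error rate for this event, so there is no figure of the plan's to reproduce.

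**Inputs from the documents.** 100 enrolled (9.2), allocated 1:1 (6.3), so 50 per arm. Event if SBP is at least 200, or the rise exceeds 40 mmHg, within 1 hour of study drug (8.3.1). No drug or placebo in controls (2.2, 4.2). Iron infused over 1-2 hours; EPO given subcutaneously, and without iron when ferritin is above 1000 ng/ml (6.1.1, 2.3.1).

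**1. Structural zero.** Controls have no administration time, so their count is 0 of 50. For k active events against 0:

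- Two-sided Fisher p = 2 × C(50,k) / C(100,k). For k = 5: 2 × 2,118,760 / 75,287,520 = 0.056. For k = 6: 2 × 15,890,700 / 1,192,052,400 = 0.027.
- Uncorrected chi-square = 100k / (100 − k). For k = 4: 400 / 96 = 4.17, p = 0.041.

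Both tests are my choice, since 9.4.4 names none. If the chance of such a swing without drug effect were 5%, 10% or 20% per patient (assumed), the probability of 6 or more active events, from the binomial with n = 50, would be 4%, 38% or 95%.

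**2. No floor on the rise.** In whole mmHg, the lowest pressure that counts as a rise is the start plus 41:

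- from 85: 126
- from 90: 131
- from 98: 139

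So any start at or below 98 can be flagged with SBP under 140. No criterion in 5.1 or 5.2 excludes a low starting pressure.

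**3. Mismatch with section 2.3.3.** A rise from 160 to 199 is 39 mmHg and stays below 200, so it is not an event, although 199 lies in the uncontrolled range of 2.3.3. SBP 185 with DBP 125, from a start of 145 or more, is not an event either, although DBP is above 110.

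**4. Reference time.** A patient given EPO alone has no infusion. With both drugs, iron goes first; read literally, the reference pressure is then taken at least 1-2 hours before the hour after EPO.

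**5. Window.** The general recording period in 8.3.4 does not help, because this item's own definition ends after one hour.

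**6. How often would the rise rule fire with no drug effect?** This rests on assumptions: normally distributed SBP around a stable mean; correlation ρ per 15-minute step, decaying as ρ to the power of the number of steps; one reading at infusion start; a 90-minute infusion; and four readings 15, 30, 45 and 60 minutes after it ends. The quantity is P(maximum of the four − start > 40), from one million simulated patients per value of ρ.

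| ρ per 15 min | SD 10 | SD 15 | SD 20 |
|---|---|---|---|
| 0.3 | 0.8% | 8.4% | 19.6% |
| 0.6 | 0.6% | 7.0% | 16.7% |
| 0.8 | 0.3% | 4.4% | 12.1% |
| 0.9 | 0.03% | 1.6% | 6.4% |

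Multiplied by 50, the extremes are 0.02 and 9.8 patients. The result depends heavily on ρ: at 0.6, the correlation between the start and the first later reading is 0.6^7 = 0.03, so the two are almost unrelated; at 0.9 it is 0.9^7 = 0.48.

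**The case against.** The best defense is that this is an administration reaction. It stands beside study drug infusion reactions, which have the same zero in controls. The list is restricted deliberately because ICU patients have many unrelated events, and one hour matches the observation that section 2.3.3 prescribes after each drug. That stands as a reason for the window. It does not rescue 9.4.4, which exempts neither item from the comparison.

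Four stronger readings are tempting, and the documents do not support them:

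- **That missed hypertension would go unrecorded.** Section 7.1 says new clinically relevant findings will be reported as adverse events, and the serious-event definition in 8.3.2 could catch a serious late episode. These routes are partial: neither names hypertension or sets a threshold, and 7.1 sits uneasily with the restricted list in 8.3.1.
- **That a particular number of false events will occur, far above the protocol's own estimate.** The documents give neither the variability nor the correlation of pressure. The below-1% figure is also not the only benchmark, since 2.3.1 puts high blood pressure among minor reactions at below 10%.
- **That the result cannot inform the larger trial.** Section 4.2 expects that trial to have resources for placebo, and an item timed from administration could then occur in both arms.
- **That the limits in 2.3.3 are the right ones for the event.** That table concerns eligibility, and its hypertension criterion is missing from 5.2. An entry limit need not equal an acute-reaction limit.

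The reference-time point is also softened: section 2.3.3 uses post-infusion wording when describing EPO, so infusion start may be meant as start of administration. Finally, severity and relatedness are graded (8.3.3), so a pressure recovery could be classed as mild and unrelated. It would still be counted.

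**Conclusion.** The point holds as a fault in one safety item and in its planned comparison. The structural zero follows from the text alone, as do the missing floor, the absent diastolic criterion, the systolic limit that differs from 2.3.3 (200 against 190) and the one-hour closure. The reference time is at least ambiguous for patients given EPO without an infusion.

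The size of any distortion is not known. With SBP SD 10-20 mmHg and 15-minute correlation 0.3-0.9, both assumed, the no-effect flag rate runs from under 0.1% to about 20%. At the low end the problem is one of principle; at the high end the table could show a nominally significant difference with no drug effect. The primary endpoint, its analysis and the sample size are untouched.

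**What to change.** 1. In 9.4.4, report the one-hour item descriptively for the active arm only, as an administration reaction outside the between-group comparison. The same sentence can cover study drug infusion reactions.
2. If hypertension is to be compared between arms, record it by one definition in both arms over a common window from randomization.
3. In 8.3.1, define the reference as the last pressure before each study drug, including EPO given without iron.
4. Do not count a rise alone without an absolute level. The sponsor should reconcile the thresholds in 8.3.1 and the 2.3.3 table with the exclusion list in 5.2, and state whether diastolic pressure counts. No particular threshold is proposed here.

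The cost is protocol and case report form wording. Section 8.2 already provides standard ICU monitoring for all subjects and daily record review for adverse events, so step 2 adds only slightly more abstraction in controls.
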